### 6.1.1 Inclusion Criteria

The decision to prescribe either Humira or MTX must be made prior to the decision to enroll a patient in the registry. A patient will be eligible for participation if he/she meets the following criteria:

1. For a patient enrolling into the Humira arm; a pediatric patient diagnosed at any time with moderately to severely active polyarticular or polyarticular-course JIA (defined as arthritis affecting ≥ 5 joints at the time of diagnosis of polyarticular or polyarticular-course JIA) who has been prescribed Humira therapy according to the locally approved Humira product labeling and meets one of the following criteria:
  - a. Enrolled patients are 4 to 17 years of age as per approved Humira product label with the addition of polyarticular JIA patients 2 to < 4 years of age in countries with available local approval for this group of patients at the time of consent to the registry.
  - b. Newly initiated (within 24 months of registry entry) on Humira therapy and has received continuous (no more than 70 consecutive days off drug) Humira therapy, and the physician can provide available source documentation of SAEs, AEs of Special Interest, and dosing information since initiation of therapy;
  - c. Or is entering after participation (within 24 months of registry entry or, if longer, continuously treated at the same site) in an AbbVie Humira sponsored study, regardless of age or the number of joints with symptoms of polyarticular JIA, and has received continuous (no more than 70 consecutive days off drug) Humira therapy and the physician can provide available source documentation of SAEs, AEs of Special Interest, and dosing information since initiation of therapy.
2. For a patient enrolling into the MTX arm; a pediatric patient diagnosed at any time with moderately to severely active polyarticular or polyarticular-course JIA (defined as arthritis affecting ≥ 5 joints at the time of diagnosis of polyarticular or

polyarticular-course JIA) who is prescribed MTX therapy alone or in combination with other DMARDs according to the local product labeling (initiated treatment within 24 months of registry entry) and has received continuous therapy and the physician can provide available source documentation of SAEs, AEs of Special Interest, and dosing information since initiation of therapy.

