#### **6.6.6 Physician Global Assessment and Patient Reported Outcome Measurements**

Information about the effectiveness of Humira or MTX therapy will be provided by the patient's parent or guardian and their physician. Patients and/or parents will complete the questions directly on the paper case report form (CRF) and the CRF pages will be

considered source documents. Effectiveness of therapy provided by the patient will be collected with clinical assessments beginning with the enrollment visit, at regularly scheduled visits which are closest to Months 1 and 3 (if applicable) and 6 and then every 6 months through Year 5. The following clinical assessments will be used: physical function of the Disability Index of Childhood Health Assessment Questionnaire (DICHAQ), and Parent's Global Assessment of Patient's Disease Activity (VAS) and Parent's Assessment of patient's pain (VAS). Effectiveness of therapy provided by the physician will be collected through the Physician's Global Assessment of Disease Activity (VAS).

The Child Health Questionnaire (CHQ-PF50) in [Appendix G](#) will be used to assess quality of life for children with polyarticular JIA through Year 5.

Physician Global Assessment and Patient Reported Outcome Measurements will not be collected after the completion of Year 5.

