### **10.4 Effectiveness Analyses**

Effectiveness data will be analyzed as observed, as this is an observational registry. The number of patients with non-missing baseline and visit values, baseline mean, visit mean, mean and standard deviation of change from baseline will be provided for continuous variables. Counts and percentages will be provided for categorical variables.

The effectiveness data will be summarized for the All Treated Patient Population (from the first dose in the registry).

The baseline measurements used in the effectiveness tables for this registry are measurements on or before the first day in the registry, except that for the subjects who are rolled over from a prior AbbVie study (Study DE038 and Study M10-444), the baseline measurements will be the baseline measurements collected in the prior study (Study DE038 and Study M10-444).

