##### **10.4.1.1 Definition PedACR30 Response**

A PedACR30 response will be defined as:

30% improvement in at least three of the six polyarticular JIA core set variables and

30% worsening in not more than one of the six remaining polyarticular JIA core set criteria.

The percent change will be calculated as:

$$100 \times (\text{Value} - \text{Baseline}) / \text{Baseline}$$

Improvement of a core set of variables by ≥ 30% is defined as a percent change from Baseline less than equal to –30% and worsening of a core set of variables by ≥ 30% is defined as a percent change from Baseline greater than or equal to 30%.

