#### **10.4.2 Analysis of Effectiveness for Intermittent Treatment with Humira**

The objective for analyses of pre-TI and post-TI effectiveness is to determine whether patients can recover pre-TI effectiveness once Humira treatment is reinitiated after the treatment interruption. The analytic approach is based on results from the polyarticular JIA development program which demonstrated that most of the efficacy of Humira in polyarticular JIA is achieved within 12 weeks after initiating treatment.

Effectiveness analyses will be performed only with patients who complete at least 12 weeks of treatment before the TI. Patients need to have at least one visit collecting effectiveness data after the TI. Effectiveness variables will be summarized at 12 weeks after the first dose of the pre TI period and compared to the results at 12 weeks after the first dose of the post-TI period.

If effectiveness results are not available at 12 weeks post-TI, then:

For patients whose last effectiveness assessment is before Week 12 of the post-TI period, the last post-TI effectiveness assessment prior to discontinuation will be carried forward.

For patients whose last effectiveness assessment is after Week 12 of the post-TI period, the first post-TI effectiveness assessment after Week 12 will be used.

A comparison of the best response (measured by PedACR 30) in the same patient before and after TI will be provided.

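### Pooled change from baseline and PedACR rates mix change since treatment start (roll-overs) with change since registry entry (patients already on drug)

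*Supplement*

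**What the plan says.** **Baseline.** Section 10.4 gives a general rule: "The baseline measurements used in the effectiveness tables for this registry are measurements on or before the first day in the registry". It makes one exception, for patients from DE038 and M10-444, for whom "the baseline measurements will be the baseline measurements collected in the prior study (Study DE038 and Study M10-444" applies. The general rule is anchored to registry entry, not to first dose. It does not say which value is taken if several exist.

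**Who can enter.** Section 6.1.1 admits Humira-arm patients who are "Newly initiated (within 24 months of registry entry) on Humira therapy and has received continuous" therapy. The MTX criterion is parallel: "initiated treatment within 24 months of registry entry) and has received continuous therapy". Under Section 6.1, patients from the prior Humira studies continue in the Humira arm.

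**What is collected.** Under Section 6.6.6, effectiveness data are "collected with clinical assessments beginning with the enrollment visit". The retrospective request in Section 6.6.2 covers SAEs, adverse events of special interest and drug exposure. It does not list effectiveness scores.

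**Speed of response.** Section 10.4.2 states that "most of the efficacy of Humira in polyarticular JIA is achieved within 12 weeks after initiating treatment". For MTX, Section 3.0 puts the usual onset of response at 3 to 6 months.

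**Analysis.** Section 10.4 summarises effectiveness in the All Treated Population. Sections 10.4.1 to 10.4.1.2 apply change from baseline and PedACR30/50/70/90 to it. PedACR rests on 100 × (Value − Baseline)/Baseline for each of six core variables. No split by roll-over status or pre-registry exposure is stated.

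**The concern.** The word baseline stands for two different things in one table. For a roll-over it is the start of an earlier study, presumably before the drug effect. For a patient who has been on drug for many months it is a value that may already carry most of that effect. Two children with the same disease course can then contribute very different changes, and different responder status, solely because of the route by which they entered.

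Long-term effectiveness is the secondary objective, with MTX patients as the reference group (Section 5.0). Prior-study roll-overs exist only in the Humira arm, so a descriptive look at Humira beside MTX on change or PedACR would partly compare entry routes. This follows from a rule the protocol states outright, not from a detail it leaves open.

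**Working it through.** The plan gives no target or power for effectiveness, so there is no figure of its own to reproduce here. Its one power statement (about 97%, Section 10.6) concerns serious infections and does not depend on the baseline rule.

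**Step 1. Which baseline each patient gets**

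| Entry route | Baseline under Section 10.4 | What a change measures |
|---|---|---|
| DE038 or M10-444 roll-over (Humira arm only) | Prior study's baseline | Change since the start of the prior study |
| New patient, first dose at or after the baseline value | Registry entry | Change since treatment start |
| MTX-to-Humira switcher assessed before first Humira dose | Entry to the Humira arm | Change since Humira start |
| New patient already on Humira or MTX (up to 24 months) | Registry entry | Change since entry, on treatment |

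The 24-month window is long beside 12 weeks (Humira) and 3 to 6 months (MTX). Many entry values in the last row may therefore already be treated values.

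**Step 2. One component, same current state.** The scores are assumed and do not come from the documents: a 100 mm VAS of 60 before treatment and 20 at the visit in question.

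- Baseline 60: (20 − 60)/60 = −67%
- Baseline 40: (20 − 40)/40 = −50%
- Baseline 30: (20 − 30)/30 = −33%
- Baseline 20: (20 − 20)/20 = 0%

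The child is in the same state in every line. An on-treatment baseline makes the 30% threshold harder to reach but does not rule it out. PedACR30 needs three of six variables, so this shows the direction for one component and does not settle a response.

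**Step 3. Effect of the mix on the pooled figures.** Let w be the roll-over share, and for simplicity let all others be already on drug at entry. The documents do not give w, so I take 10% to 50%.

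- Mean VAS change, others entering at 20: −40w + 0(1 − w), which is −4 at w = 10% and −20 at w = 50%.
- Mean VAS change, others entering at 30: −40w − 10(1 − w), which is −13 and −25.
- PedACR30 with assumed rates of 80% (roll-overs) and 20% (already on drug): 0.8w + 0.2(1 − w), which is 26% and 50%.
- PedACR30 with 40% in place of 20%: 0.8w + 0.4(1 − w), which is 44% and 60%.

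**Step 4. Effect on the reference comparison.** The MTX arm has w = 0, so on the same assumptions its rate is 20% (or 40%). The Humira arm would then look better by 26 − 20 = 6 to 50 − 20 = 30 points (or 44 − 40 = 4 to 60 − 40 = 20 points) with no difference in disease course. These ranges illustrate the mechanism. They are not estimates for this registry.

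**The case against.** The strongest reply is that effectiveness here is secondary and descriptive, with no test or threshold, and that much of what one would want is already planned. Section 10.4 prints baseline and visit means beside the change. Section 10.4.1 gives full distributions by visit. JADAS level and inactive disease are states that need no baseline. This stands, and it confines the problem to pooled change from baseline and PedACR. A reader might infer that the effectiveness results as a whole are uninterpretable, and the documents do not support that.

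Second, the general rule allows a value before the first registry day, and note e to Table 1 mentions medical assessments from the first commercial Humira dose. A pre-treatment value could therefore exist for some patients. But Section 10.4 does not say it would be preferred, so this is a reason to clarify the rule.

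Third, no SAP is shown. It might stratify, but the deferral to it appears in Section 10.4.1.4, for other endpoints, while the Section 10.4 rule is specific. The formula has no value when a component's baseline is 0, and a reader might count that as a further error. Handling of that case is commonly left to an SAP, so it is not one here.

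Fourth, a reader might assume that entry is uniform over 24 months and conclude that about 88% of non-roll-overs (1 − 12/104) enter after Week 12. The documents do not support this. No entry distribution is given, the 12-week statement is about Humira only, and Month 1 and Month 3 visits are planned for non-roll-overs, which is compatible with many starting drug near entry.

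**Conclusion.** The point holds for pooled change from baseline and PedACR30/50/70/90 in the All Treated Population. As written, these combine change since treatment start with change since registry entry. Patients already controlled at entry are less likely to be counted as responders, and the pooled rate moves with the entry mix. The mix differs by arm because prior-study roll-overs enter only the Humira arm.

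The size is unknown, because neither the roll-over share nor the distribution of prior exposure is given. The 26% to 50% range rests on assumed response rates and shares. That the prior-study baseline precedes treatment is also an inference: DE038 had a placebo-controlled double-blind period (Section 10.2), and the plan does not say which of its baselines applies.

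A reader might infer that a controlled patient cannot show a 30% improvement. That goes too far, as the entry values of 40 and 30 in Step 2 show. Visit means, JADAS level, inactive disease status and the safety sample size are not affected. The plan should be changed, since the fault is in a stated rule and the remedy is cheap.

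**What to change.** 1. Define baseline relative to the first dose of the arm's drug, using a pre-dose value where one is available, and say which value is taken if there are several.
2. State which DE038 baseline applies.
3. Report change from baseline and PedACR30/50/70/90 separately for:
   - (a) prior-study roll-overs;
   - (b) patients whose baseline is on or before first dose, including MTX-to-Humira switchers assessed before their first Humira dose;
   - (c) patients already on drug at entry, by duration of pre-registry exposure.
4. For group (c), rely on absolute status by visit (JADAS, active joints, DICHAQ, inactive disease), and state that PedACR is not to be read as response to starting treatment.

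The cost is analysis wording, some extra tables and smaller groups in each. No new data are needed to form the groups: pre-registry exposure is requested under Section 6.6.2, and Section 10.2 already uses the first recorded dose to compute total exposure.

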#### **10.4.1 Juvenile Idiopathic Arthritis Core Set of Variables**

Each of the following core polyarticular JIA component scores, change from the Baseline will be summarized by summary statistics (number of patients, mean, 95% confidence interval, standard deviation, first quartile, median, third quartile, minimum, maximum) at each visit:

- a. Physician's global assessment of patient's disease activity by visual analog scale (VAS) (100 mm VAS, 0 = very good and 100 = very bad)
- b. Parent's global assessment of patient's disease activity by VAS (100 mm VAS, 0 = very well and 100 = very bad)
- c. Number of active joints (joints with swelling not due to deformity or joints with limitation of passive motion [LOM] and with pain and/or tenderness)
- d. Number of joints with LOM
- e. Disability Index of Childhood Health Assessment Questionnaire (DICHQAQ)
- f. CRP or ESR if collected and available only when part of the physician's site routine care.

##### **10.4.1.1 Definition PedACR30 Response**

A PedACR30 response will be defined as:

30% improvement in at least three of the six polyarticular JIA core set variables and

30% worsening in not more than one of the six remaining polyarticular JIA core set criteria.

The percent change will be calculated as:

$$100 \times (\text{Value} - \text{Baseline}) / \text{Baseline}$$

Improvement of a core set of variables by ≥ 30% is defined as a percent change from Baseline less than equal to –30% and worsening of a core set of variables by ≥ 30% is defined as a percent change from Baseline greater than or equal to 30%.

#### **10.4.1.2 Definition of PedACR 50 and PedACR 70 and PedACR 90 Response**

PedACR50, 70 and 90 levels of response will be defined by using improvement percentages of 50, 70 and 90, respectively, in at least 3 of the 6 core set parameters with worsening of 30% or more in no more than 1 of the 6 core set parameters. The effectiveness individual indicators and the PedACR30/50/70/90 response will be summarized descriptively at each registry time point ([Figure 1](#) and [Figure 2](#)).

#### **10.4.1.3 Definition of JADAS**

The juvenile arthritis disease activity score (JADAS) is defined as the sum of the scores of its four components. The four components are:

- a. Physician's global assessment of patient's disease activity measured on 0 – 10 cm VAS
- b. Parent's global assessment of patient's disease activity measured on a 0 – 10 cm VAS
- c. Number of active joints (joints with swelling not due to deformity or joints with limitation of motion [LOM] and with pain on passive motion, tenderness or both)
- d. Normalized ESR or CRP if collected and available only when part of the physician's site routine care.

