**Table 1. Registry Activities (Continued)**

- f. AESI, SAEs and pregnancies will be collected from Year 1 through Year 5. From Year 6 through Year 10 SAEs, a subset of AESI that includes congestive heart failure (CHF), malignancies, AEs at least possibly related to and/or leading to discontinuation of registry treatment and pregnancies will be collected. For patients that participate in the direct to HCP follow-up process AESI, hospitalizations, surgeries, and death will be collected annually from Year 1 through Year 5 and malignancies, CHF, hospitalizations, surgeries and death will be collected annually from Year 6 to Year 10. For polyarticular JIA patients from 2 to < 4 years of age while in the registry AESI, SAEs and pregnancies will be collected through Year 10 and those who participate in the direct to HCP follow-up process will have AESI, hospitalizations, surgeries and death collected annually through Year 10.
- g. Provide local lab values including but not limited to ESR, CRP, anti-nuclear antibody (ANA), and any labs related to SAE's or AEs of Special Interest (i.e., CPK, presence of lupus anticoagulants or anticardiolin antibodies). The assessments will be collected at baseline and afterwards only when part of physician's site routine care.
- h. Patients who develop an Adverse Event of Special Interest (AESI) or SAE while in the registry will be followed throughout the patient's participation in the registry or direct to HCP follow-up process until satisfactory conclusion or until 70 days following the last registry dose (whichever is longer). Follow-up received on ongoing SAEs and/or AESI post registry conclusion should be reported using standard Post Marketing Reporting.

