#### **6.6.8 Laboratory Assessments**

There are no required laboratory tests for this registry. Laboratory tests, such as chemistry, hematology, and erythrocyte sedimentation rate (ESR), will be collected when part of the physician's site routine care. However to assess the PedACR score, it is recommended that CRP and/or ESR be provided where available. If available as part of routine care, anti-nuclear antibody (ANA) and past or current genetic testing results HLA-B27 will be collected. There is no central laboratory for this registry; therefore all lab assessments will be conducted by a local laboratory at the physician's discretion and collected where available.

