### **6.6.9 Inactive Disease Assessment**

The inactive disease assessment will be recorded starting at the enrollment visit and at each registry visit thereafter through Year 5. A patient has inactive disease if he/she meets the following:

- No active arthritis
- No fever
- No rash
- No serositis
- No splenomegaly
- No generalized lymphadenopathy attributable to JIA
- No active uveitis in connection with JIA
- Normal ESR or CRP level only when part of the physician's site routine care
- Physician's global assessment of disease activity indicating clinical disease quiescence.

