### 6.7.1 Effectiveness Variables

Information to evaluate the effectiveness of Humira or MTX therapy will be collected from patients and their physicians if part of routine clinical assessment. In the event Humira therapy is interrupted, effectiveness variables will be collected during the interruption.

The effectiveness of therapy evaluation provided by the patient or parent will be collected with clinical assessments as discussed in Section 6.6.6. The following clinical assessments will be used:

- Parent's Assessment of Patient's Pain (VAS)
- Parent's Global Assessment of Patient's Disease Activity (VAS)
- Physical function of the DICHAQ
- Child's Quality of Life CHQ-PF50

Effectiveness of therapy provided by the physician will be collected through the Physician's Global Assessments, if part of routine clinical assessment. The following assessments will be collected:

- Physician's Global Assessment of Disease Activity (VAS) ([Appendix F](#))
- Joint pain and swelling
- Number of active joints
- Number of joints with limitation of passive motion (LOM)
- Number of joints with pain on passive motion (POM)
- CRP and/or ESR level only when part of the physician's site routine care

Patients may also be evaluated for inactive disease. The criterion for inactive disease includes the following:

- No active arthritis
- No fever

No rash  
No serositis  
No splenomegaly  
No generalized lymphadenopathy attributable to JIA  
No active uveitis in connection with JIA  
Normal ESR and/or CRP level only when part of the physician's routine care  
Physician's global assessment of disease activity indicating clinical disease quiescence.

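### Inactive disease is judged on nine criteria when ESR or CRP was measured and on eight when it was not, and JADAS has the same conditional component without a rule for its absence

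*Supplement*

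**What the plan says.** **Inactive disease.** Section 6.6.9 introduces its list with "A patient has inactive disease if he/she meets the following" and gives nine items. Eight are clinical: seven signs that must be absent, and a physician's global assessment showing quiescence. The ninth is laboratory-based: "Normal ESR or CRP level only when part of the physician's site routine care". Section 6.7.1 repeats the list with slightly different wording for that item: "Normal ESR and/or CRP level only when part of the physician's routine care". The assessment is recorded at enrollment and at each registry visit through Year 5, and Section 10.4.1.4 says it will be analysed.

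**JADAS.** Section 10.4.1.3 states that the score "is defined as the sum of the scores of its four components". The first is "Physician's global assessment of patient's disease activity measured on 0 – 10 cm VAS", the second is the parent's global on the same scale, and the third is the active joint count. The fourth is "Normalized ESR or CRP if collected and available only when part of the physician's site routine care". The section gives no normalisation formula and no rule for a visit at which this component is absent.

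**Availability of the marker.** Section 6.6.8 says "There are no required laboratory tests for this registry", although it recommends that CRP and/or ESR be supplied where available. Note g to Table 1 says of laboratory values: "The assessments will be collected at baseline and afterwards only when part of physician's site routine care". Section 10.4 analyses effectiveness data as observed. The statistical analysis plan is not among the documents shown.

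**The concern.** An outcome definition should ask the same question of every patient at every visit. Here the question depends on whether blood was drawn. For inactive disease, a patient who meets the eight clinical criteria but has a raised marker fails if tested and passes if not. The proportion inactive therefore mixes disease state with testing practice. It can shift between visits, sites or arms with no difference in disease.

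JADAS is exposed to a related problem, depending on how the score is computed when the marker is missing. All components are non-negative, so a sum over whatever is available cannot exceed the full sum. If a baseline with the marker were compared with a visit without it, part of the change could be an artefact in the direction of improvement.

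Long-term effectiveness, with MTX patients as a reference group, is the registry's secondary objective (Section 5.0). These are descriptive outcomes, but readers will compare them over time and between arms.

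**Working it through.** The plan states no figure for this point, so there is nothing to reproduce. All numerical inputs below are assumptions.

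**Inactive disease**

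Inputs:
- p8 = probability of meeting the eight non-laboratory criteria; assumed 0.40.
- q = probability of a normal marker among patients who meet those eight; assumed 0.85, varied from 0.70 to 1.00.
- t = proportion tested; 90% and 50% for illustration. Testing is taken as unrelated to the marker value.

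Formulas:
- Tested patients: P(inactive) = p8 × q.
- Untested patients: P(inactive) = p8. Since q ≤ 1, this is never smaller.
- Whole group: P(inactive) = p8 × (t × q + 1 − t).

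With q = 0.85:
- Tested: 0.40 × 0.85 = 34%. Untested: 40%.
- 90% tested: 0.40 × (0.765 + 0.10) = 0.40 × 0.865 = 34.6%.
- 50% tested: 0.40 × (0.425 + 0.50) = 0.40 × 0.925 = 37.0%.
- Difference: 2.4 percentage points with identical disease. Equivalently, 0.40 × (1 − 0.85) × (0.90 − 0.50) = 0.024.

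| q | Tested | Untested | Group 90% tested | Group 50% tested |
|---|---|---|---|---|
| 0.70 | 28% | 40% | 29.2% | 34.0% |
| 0.85 | 34% | 40% | 34.6% | 37.0% |
| 0.95 | 38% | 40% | 38.2% | 39.0% |
| 1.00 | 40% | 40% | 40.0% | 40.0% |

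The artefact disappears only if every clinically inactive patient has a normal marker, or if testing frequency is the same in the groups or visits compared.

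**JADAS, if summed over available components**

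Inputs: physician's global 3, parent's global 3 and 4 active joints, all assumed. The marker score is assumed to run from 0 to 10, since the plan gives no range.

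- Three components: 3 + 3 + 4 = 10.
- Four components, with marker score 0, 1, 2, 4 or 10: 10, 11, 12, 14 or 20.
- The shortfall at an untested visit equals the marker score that was not measured, and is zero when that score is zero.

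For change from a tested baseline, let m0 be the marker score at baseline and m1 the unmeasured score at the visit, with the clinical components unchanged. The true change is m1 − m0 and the apparent change is −m0, so the error is −m1. If m0 = m1 = 2, the score goes from 12 to 10, an apparent fall of 2/12 = 17% with no real change. If the marker has fallen to zero at the visit, the apparent change is correct.

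**JADAS, if a missing component makes the score missing**

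There is then no shortfall, but the score exists only at visits where blood was drawn.

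**The case against.** The strongest objection concerns JADAS. The section defines a sum of four components and nowhere tells the analyst to add three when the fourth is absent. Together with as-observed analysis, the plain reading is that such a visit has no score. How to handle a missing component is also ordinary analysis-plan content. This stands: a reader might infer that the plan makes untested patients score lower, but the documents do not say so.

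A reader might also infer from note g that baseline is always tested and follow-up is not, so that change is systematically tilted toward improvement. Section 6.6.8 requires no test and makes no exception for baseline, and no testing frequencies are given. The tilt is possible, not established. Moreover, if blood is drawn mainly when disease is active, untested visits would tend to have low marker scores. Section 3.0 notes that ESR and CRP fall quickly after Humira is started. Both points shrink the error, and its lower bound is zero.

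A third tempting inference is that testing differs between the Humira and MTX arms. No section says that it does.

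For inactive disease the objection is weaker. Section 10.4.1.4 leaves details to the analysis plan, but the unequal criteria are written into Sections 6.6.9 and 6.7.1 as the definition. An analysis plan that follows them as written would keep the inequality.

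**Conclusion.** The inactive-disease point holds on the wording alone: untested patients are judged on eight criteria and tested patients on nine, so at equal disease the untested are called inactive at least as often. The size depends on figures the documents do not give. Under the assumed inputs it is 6 percentage points between tested and untested patients, and 2.4 points between groups tested 90% and 50% of the time. With q between 0.70 and 1.00, that second difference ranges from 4.8 points to none.

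The JADAS point is conditional. One component depends on routine testing, and the protocol shown does not say how the score is formed without it. A lower score follows only if components are summed as available and the unmeasured marker would have been above zero. The documents support neither a guaranteed drift toward improvement nor a bias between arms.

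Both outcomes are secondary and descriptive. The primary safety objective is untouched, as is the sample size, which rests on serious infections. This is a cheap improvement worth making, not a flaw that threatens the registry's main conclusion.

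**What to change.** - **Inactive disease (6.6.9 and 6.7.1).** Report it on the eight non-laboratory criteria for all patients. Report the version that also requires normal ESR/CRP separately, with tested patients as the denominator. Give the proportion tested by arm and visit. Use one wording for the laboratory item in both sections.
- **JADAS (10.4.1.3).** Compute change in the four-component score only for patients with the same marker, ESR or CRP, at baseline and at that visit. State that three- and four-component sums are never compared. Add a three-component clinical sum for all patients as a supportive analysis. Replacing the cited four-component instrument as the main score would be a trade-off and is not needed.

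The cost is a few lines of wording and one extra table per endpoint. No new assessments are needed, provided the individual inactive-disease criteria are held in the database and not only the overall status; the forms are not shown, so this should be checked. The downside is fewer patients in the four-component JADAS change, and the proportion tested will show how many.
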